4.6.2 Per Protocol Sample

The per-protocol sample will include only those randomized patients who stayed on the study protocol until successful liberation from IMV, 90 days, or death, whichever came first. The per-protocol sample will exclude subjects who were withdrawn from the study, or spent more than 48 hours in a non-protocolized mode of ventilation duringthe first 21 days (neither PAV, nor PSV, nor CPAP, nor AC). Note that use of assist-control mode in either volume or pressure control was allowed per protocol in each arm of the study. The per-protocol sample will also exclude patients who were transferred to another centre or ward prior to completing the study protocol, with the exception of patients who were transferred for palliation and died within 7 days of transfer; such patients will be considered to have completed the study protocol, and will be included in the per protocol sample.

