10.3 Randomization & Blinding**10.3.1 Randomization**

Participants will be randomized once eligibility is determined, by having satisfied all of the inclusion criteria and none of the exclusion criteria, have passed the Pressure Support Trial and either not meeting Weaning Criteria or failing the ZERO CPAP Trial or failing the SBT. Each participant in this study will be randomized to either PSV or PAV+ in a 1:1 ratio in Medidata RAVE.

Participant allocation to procedure group will be via variable block randomization with varying block sizes and stratified by site to minimize the likelihood of predicting the next procedure assignment. Randomization will be attained using computer generation sequence methodology, ensuring that the randomization methodology and the generated allocation sequence are concealed from the investigator and participants.

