12.0 Statistical Plan

12.1 Sample Size Determination

Primary and secondary outcomes will be analyzed at the conclusion of the trial.

A table of sample sizes for time from randomization to first successful extubation/liberation is shown below. These calculations incorporate death by treating death as censoring. The current hazard rate for death is used in this calculation. The final column is obtained by dividing the "Total N" column by 0.95 to account for the 5% dropout. Assuming this increase is sufficient to observe the required number of events in the presence of the drop-out, it should be a reasonable target.

All calculations are using 80% power and 2-sided Type I error of 5%. Exponential survival is assumed for the purposes of hazard calculations. The expected median time to extubation in PAV is determined from the PSV value by converting to the hazard scale, multiplying by the hazard ratio and converting back to time.

Median Time (PSV)	Median Time (PAV)	Difference	Hazard Ratio	Required Events	Total N	Total N (5% lost)
7.40	6.17	1.23	1.20	944	1095	1153
7.40	5.92	1.48	1.25	630	729	768
7.40	5.69	1.71	1.30	456	526	554
7.50	6.25	1.25	1.20	944	1097	1155
7.50	6.00	1.50	1.25	630	731	770
7.50	5.77	1.73	1.30	456	527	555
7.55	6.29	1.26	1.20	944	1098	1156
7.55	6.04	1.51	1.25	630	731	770

7.55	5.81	1.74	1.30	456	528	556
7.60	6.33	1.27	1.20	944	1099	1157
7.60	6.08	1.52	1.25	630	732	771
7.60	5.85	1.75	1.30	456	528	556
7.70	6.42	1.28	1.20	944	1101	1159
7.70	6.16	1.54	1.25	630	733	772
7.70	5.92	1.78	1.30	456	529	557

As planned a priori, we used aggregate, blinded data from the first 120 patients to re-estimate our sample size. Using a time to event analysis, median time to successful liberation in the entire cohort was 6.8 days. The minimum clinically important difference in time to successful liberation is deemed to be 1.0 day. Using a hazard ratio of 1.30, to demonstrate a reduction in the median duration of ventilation by 1.78 days (assuming 7.70 days versus 5.92), alpha of 0.05 (two-sided) and a power of 80%, requires 529 patients. Anticipating a maximum loss to follow-up (e.g. consent withdrawn) rate of 5%, 558 patients (279 per group) should be randomized in the study. Using a hazard ratio of 1.25, to demonstrate a reduction in the median duration of ventilation by 1.51 days would require 770 patients (385 per group) to be randomized in the study.

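### The per-protocol sample deletes whole patients for events after randomization, and its 48-hour mode rule selects on the primary outcome, so unequal exclusions would bias its hazard ratio in either direction

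*SAP*

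**What the plan says.** SAP 4.6.2 restricts the per-protocol sample to patients who stayed on protocol until liberation, day 90 or death. Three post-randomization events remove a patient altogether:

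- Withdrawal, or too long in another mode: "The per-protocol sample will exclude subjects who were withdrawn from the study, or spent more than 48 hours in a non-protocolized mode" within the first 21 days. PAV, PSV, CPAP and A/C all count as protocolized, and no arm is named.
- Transfer to another centre or ward before the protocol is completed, "with the exception of patients who were transferred for palliation and died within 7 days of transfer"; those patients stay in.

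Neither censoring at the deviation nor weighting is offered. The weighting in SAP 3.3 covers missing outcomes in non-survival analyses only.

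The role of the sample is unclear. SAP 4.6 names both intention-to-treat and per-protocol analysis, and 4.4 promises per-protocol counts in the flow diagram. SAP 4.6.1 assigns all analyses to the intention-to-treat sample, and sections 6.1 to 6.6 give the per-protocol sample no outcome, model or role.

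**The concern.** The primary outcome is time to successful liberation. The mode rule needs more than 48 hours of ventilation after randomization, so a patient liberated on day 1 or 2 is certain to be kept while a slow weaner is exposed to exclusion. Deleting the whole patient then removes long ventilation times from the arm, and that arm appears to wean faster than it did.

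If both arms lose the same share in the same way, the distortion cancels. If they do not, a hazard ratio away from 1 appears without any treatment effect. A difference is conceivable here: the trial is open-label, PAV+ needs one of two specific ventilators (Protocol 8.1.1), and PSV may be given on any suitable machine (Protocol 8.2.1). At stake is a per-protocol estimate that seems to corroborate, or to contradict, the intention-to-treat result because of how the sample was built.

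**Working it through.** **The plan's own figures.** The design case is "Using a hazard ratio of 1.30, to demonstrate a reduction in the median duration of ventilation by 1.78 days (assuming 7.70 days versus 5.92" days), 80% power, two-sided 5%.

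- Events (Schoenfeld): 4(1.960 + 0.842)²/(ln 1.30)² = 456.1; the plan states 456.
- With loss: 529/0.95 = 556.8, so 557 as tabulated, and 558 when made even for 1:1 allocation.
- Death hazard: not printed. "Exponential survival is assumed for the purposes of hazard calculations", so it can be solved from 456/529 = 0.862. With liberation hazards ln 2/7.70 = 0.0900 and 1.30 × 0.0900 = 0.1170 per day, μ = 0.0163 gives (0.0900/0.1063 + 0.1170/0.1333)/2 = 0.862. This value reproduces six other table rows to within one patient.

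The documents give no figure for the size or error rate of the per-protocol sample.

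**Who cannot be excluded by the mode rule.** At the pooled median of 6.8 days (SAP 2.3), λ = 0.1019. The share liberated within 48 hours is 0.1019/0.1182 × (1 − e^(−0.2365)) = 18%.

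**Closed form.** Let λ be the liberation hazard, μ the death hazard and g the hazard of an excluding event while ventilated. The share excluded is x = g/(λ + μ + g). Those retained leave ventilation at rate λ + μ + g, in unchanged proportions of liberation and death. Their apparent liberation hazard is therefore λ(λ + μ + g)/(λ + μ) = λ/(1 − x). With no true effect:

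per-protocol HR = (1 − x_PSV)/(1 − x_PAV+)

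**The mode rule itself.** With a 48-hour delay and a 21-day window, x = e^(−2(λ+μ)) × g/(g+λ+μ) × (1 − e^(−19(g+λ+μ))). Take λ = 0.0900 and μ = 0.0163 in both arms. Assumed hazards of starting another mode of 0.005, 0.02 and 0.03 per day give x = 3.2%, 11.6% and 16.5%. The closed form then gives 0.968/0.884 = 1.10 and 0.968/0.835 = 1.16.

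Simulated trials, 279 per arm, true HR 1.00, PSV at 0.005 per day:

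| Excluded, PSV vs PAV+ | Cause-specific HR | Rejection, cause-specific log-rank | Rejection, Gray-type | Rejection, same patients censored at 48 h |
|---|---|---|---|---|
| 3% vs 3% | 1.00 | 5% | 5% | about 5% |
| 3% vs 12% | 1.09 | 15 to 16% | 8% | 5% |
| 3% vs 16% | 1.16 | 33% | 13% | 5% |

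The Gray-type test is a subdistribution log-rank with deaths kept at risk to day 90. It moves less because deletion changes the speed of leaving ventilation but not the eventual split between liberation and death.

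**Other cases** (6.8-day median, N = 558, true HR 1.00):

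- Reversed, PSV 15% vs PAV+ 5%: 0.85/0.95 = 0.89, with false harm in 21% of trials.
- Equal 10% shares, PAV+ lost while ventilated and PSV lost at random: HR 1.11, false benefit 19% (nominal 2.5%).
- Palliation exception covering an assumed 20% of exclusions, PAV+ 15% vs PSV 5%: the cause-specific HR falls from 1.12 to 1.08 and the Gray-type ratio from 1.06 to 1.00.

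**The case against.** The best defence is that no specified result depends on this sample. SAP 4.6.1 puts all analyses on intention to treat, and section 6 never uses the per-protocol set. That stands: the primary result is safe, and the risk lies in an analysis that is named but not described.

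The mode list also makes a large imbalance less likely. A clinician uneasy with PAV+ would probably turn to A/C, the protocol's fallback, or to PSV, and read literally neither triggers exclusion. This stands too; the 12% and 16% are illustrations, not forecasts. The flow diagram and the mode-deviation summaries (SAP 4.4, 4.5) would show an imbalance, though they would not correct for it.

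A reader might infer three stronger things that the documents do not support:

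- That the sample favours PAV+. The direction depends on which arm loses more patients, and nothing in the documents settles that.
- That every exclusion can only befall a patient still ventilated. This is strictly true of the mode rule alone. Withdrawal has no time limit, and ward transfer can follow extubation; whether that is before protocol completion is unclear, because Protocol 9.2 accepts successful ICU discharge while SAP 5.1 requires 7 days.
- That keeping palliative transfers only if they die manufactures a benefit. The rule depends on outcome, but it retains patients who were never liberated, which lowers apparent liberation.

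**Conclusion.** The concern holds as a defect of the per-protocol definition. Whole patients are deleted for post-randomization events, and the mode rule conditions on remaining ventilated. The bias in the cause-specific hazard ratio is about (1 − x_PSV)/(1 − x_PAV+): none at equal shares through the same mechanism, roughly 9% at 3% vs 12%, roughly 16% at 3% vs 16%, and below 1 if PSV loses more. False-positive rates rise about threefold and sixfold over 5% on a cause-specific log-rank test, and to 8% and 13% on a Gray-type version of the test named in SAP 6.1.

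These sizes rest on exponential times, a back-solved death hazard, deviations unrelated to prognosis and assumed exclusion rates. The mechanism does not depend on the assumed rates; the magnitude does. The point is worth correcting because the repair is cheap, but it does not threaten the primary analysis.

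**What to change.** Rewrite SAP 4.6.2 as a per-protocol analysis of all patients rather than a reduced sample:

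- Keep every patient from randomization. Censor when the 48-hour limit is passed, at withdrawal, or at a transfer before liberation, with the same rule in both arms.
- Apply inverse-probability-of-censoring weights. Unweighted censoring was unbiased above only because deviations were simulated independently of prognosis. Candidate covariates are already collected: those in SAP 4.7 and 6.4, and SOFA score and fluid balance during follow-up.
- Replace the 7-day exception. Count deaths known to follow a palliative transfer as competing events whatever their timing; censoring them would discard observed events.
- Define protocol completion, state that the analysis is supportive of intention to treat, and name its outcome and model in section 6.
- Report deviations by arm, reason and day.

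The cost is SAP wording and modest programming. Hours in non-protocolized modes are already recorded (SAP 4.5). The downside is that the weights need a short covariate list fixed in advance and an assumption of no unmeasured confounding of deviation and outcome.

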8.3.5.2 Re-intubation Guideline

Reintubation is performed at the discretion of the treating clinician. Time of reintubation and reason(s) for reintubation will be recorded:

Reasons for Re-intubation:

1. Cardiac arrest
2. Respiratory arrest (respiratory pauses with loss of consciousness or gasping for air)
3. Respiratory distress (see definition) or respiratory failure and NIV relatively contraindicated
4. Respiratory distress (see definition) or respiratory failure and NIV Failure
5. Decreased level of consciousness impairing ability to protect airway
6. Hemoptysis or hematemesis impairing ability to protect airway
7. Abundant secretions that cannot be effectively cleared or are associated with lobar collapse, acidosis, hypoxemia, or change in mental status
8. Clinical instability (see definition)
9. Surgical/invasive procedure requiring sedation/anaesthesia +/- neuromuscular blockade such that patient will no longer be able to sustain unassisted breathing
10. Other (specify)

If a patient remains in ICU and requires reintubation within 7 days of extubation, that patient will remain in the study, and will resume ventilation according to the assigned ventilation strategy (i.e. using A/C and PAV+ only for patients in the PAV+ arm, and using A/C and PSV only for patients in the PSV arm). Patients initially supported with assist/control mode will be switched to PAV+ or PSV according to their assigned ventilation strategy upon

meeting Criteria for Switching from A/C to PAV+ or PSV. If a patient is discharged from ICU but readmitted to ICU within 48 hours of discharge, and requires reintubation within 7 days of extubation, that patient will remain in the study and will resume ventilation according to the assigned ventilation strategy, as per above.

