2.1 Trial design

The PROMIZING study is a multi-centre, randomized, parallel assignment, open label clinical trial designed with a superiority framework. Neither the clinical team nor the study investigators will be blinded to the study intervention. The study statistician will be blind to the study arm. Allocation ratio is 1:1 to the two arms of the study. Patients randomized to the PAV+ intervention arm will follow a PAV+ ventilation protocol, where PAV+ is set to maintain respiratory muscle pressure within a target range of 5-10 cmH2O. Patients randomized to the PSV control arm will follow a PSV ventilation protocol, where PSV is set to maintain usual clinical parameters of respiratory rate and tidal volume. In both arms, patients who are not tolerating the assigned mode will be placed on assist/control ventilation, and in both arms, patients will undergo daily screening for readiness for liberation with protocolized spontaneous breathing trials.

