4.5 Adherence and protocol deviations

Protocol deviations are defined and categorized as minor or major as follows:

Type of Deviation	Category
Patient met criteria for switching from A/C to PAV+, A/C to PSV but not switched	Minor
Patient met extubation criteria but not extubated	Minor
Study timelines not followed	Minor
SBT performed with different respiratory parameters than specified	Minor
Weaning/screening algorithm not followed when patient met weaning criteria	Major
Use of non-protocolized mode	Major

To improve adherence to study interventions, the bedside clinician responsible for adjusting the ventilator (e.g., respiratory therapist, physiotherapist, physician) will complete a daily checklist which will be recorded in the RAVE database. The checklist serves as a reminder to the clinician to follow the study protocol, and also allows us to document protocol adherence. Additionally, use of any non-protocolized mode of ventilation, duration of exposure to non-protocolized mode, and reason for non-protocolized mode is recorded in the database.

Protocol deviation summary reports are presented to the DSMB at regular intervals and include:

- (a) number of deviations of each type that occurred and the category (minor, major)
- (b) number of patients with each type of deviation
- (c) total number of major and minor deviations
- (d) total number of study days
- (e) rate of occurrence, calculated as the number of deviations divided by the total number of study days, expressed as a percentage of the total number of study days, for each type of deviation and in total.

(f) Mode deviations – number of patients who used non-protocolized mode and number of hours spent on non-protocolized mode

Descriptive statistics on use of non-protocolized modes as well as intolerance of PAV+ and PSV (duration in days and percentage of time in study spent on assist/control mode) will be provided

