4.6.1 Intention To Treat Sample

All analyses will use the intention to treat sample. The intention to treat sample will be comprised of all randomized patients who started the study intervention, irrespective of compliance to their randomized group. Patients will contribute outcome data to the analysis based on the randomized group.

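### The per-protocol mode rule in SAP 4.6.2 is the same for both arms, so hours on the other arm's mode never count toward the 48-hour exclusion

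*SAP*

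**What the plan says.** SAP 4.6 plans both intention-to-treat and per-protocol analyses, and SAP 4.4 puts the number in each into the CONSORT diagram.

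SAP 4.6.2 builds the per-protocol sample in two steps. It first admits only randomized patients "who stayed on the study protocol until successful liberation from IMV, 90 days, or death, whichever came first". It then excludes those who were withdrawn or who "spent more than 48 hours in a non-protocolized mode of ventilation duringthe first 21 days (neither PAV, nor PSV, nor CPAP, nor AC"), and most of those transferred before completing the protocol. It adds that "use of assist-control mode in either volume or pressure control was allowed per protocol in each arm of the study". It says nothing comparable about PAV+ in the PSV arm or PSV in the PAV+ arm.

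The permitted modes are arm-specific elsewhere. Protocol 8.3.5.2, writing about reintubated patients, glosses the assigned strategy as "using A/C and PAV+ only for patients in the PAV+ arm, and using A/C and PSV only for patients in the PSV arm". SAP 2.1 says that in both arms "patients who are not tolerating the assigned mode will be placed on assist/control ventilation". Protocol 8.3.2 then returns them to the mode they were randomized to.

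SAP 4.5 classes "Use of non-protocolized mode" as a major deviation and reports to the DSMB the "number of patients who used non-protocolized mode and number of hours spent on non-protocolized mode". It does not define the term.

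**The concern.** The trial compares two modes, open label. PSV can be delivered on any capable ventilator, whereas PAV+ needs a specific one (Protocol 8.1.1 and 8.2.1), so drift from PAV+ to PSV is a plausible route of contamination. A per-protocol analysis in such a trial is normally expected to show the comparison among patients who received what they were assigned. A rule that counts only modes belonging to neither arm does not do that. It can drop a patient for time on an unrelated mode and pass over one who spent the same time on the comparator.

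What is at stake is the usefulness of a supportive analysis. If crossovers remain in the set, its estimate is diluted in the same direction as the intention-to-treat estimate and says little about whether contamination mattered. If they are instead removed case by case, the exclusion is discretionary in a trial whose clinicians and investigators know the allocation.

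**Working it through.** The point rests on wording, so the main check sets the texts against each other. The arithmetic only illustrates scale.

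**1. Apply the rule as written.** Take a PAV+ patient ventilated on PSV for one week, 7 × 24 = 168 hours, within the first 21 days. PSV is on the SAP 4.6.2 list, so the hours counted are 0, and 0 is not above 48. The mode rule does not exclude the patient. A patient with 49 hours in a mode not on the list is excluded. If the list held only A/C and the assigned mode (plus weaning-test time), the first patient's count would be 168, which is above 48, and the patient would be excluded.

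**2. Compare with the protocol.** Protocol 8.3.5.2 names A/C and the assigned mode only. SAP 2.1 gives A/C as the response to intolerance. SAP 4.6.2 names only A/C as allowed in each arm. None of these permits the other arm's mode, so the list does not match the protocol it is meant to enforce.

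**3. Test whether the general condition closes the gap.** The requirement to have stayed on protocol names no mode and no duration. It cannot mean zero time off protocol, because the next sentence tolerates up to 48 hours in a non-protocolized mode. Some tolerance is therefore implied, but none is stated for the opposite arm's mode. The condition leaves room to exclude a crossover but gives a programmer nothing to code.

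**4. Scale, as an illustration.** The planning effect is a hazard ratio of 1.30 with 456 required events (Protocol 12.1, SAP 2.3). As a check on that figure, the Schoenfeld formula gives 4 × (1.960 + 0.842)² / (ln 1.30)² ≈ 456.1, or 457 rounded up, so the plan's number reproduces.

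The documents give no crossover rate. Assume that a share *c* of retained patients carries the other arm's hazard for the whole period, with hazards mixing in proportion:

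- Crossover in the PAV+ arm only: HR ≈ (1 − c) × 1.30 + c.
- Crossover in both arms: HR ≈ [(1 − c) × 1.30 + c] / [(1 − c) + c × 1.30].

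| c | PAV+ arm only | Both arms |
|---|---|---|
| 5% | 1.285 | 1.266 |
| 10% | 1.270 | 1.233 |
| 20% | 1.240 | 1.170 |

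Mixing on the log scale instead, 1.30^(1 − c), gives 1.27 at 10% and 1.23 at 20% for the PAV+ arm only, so the choice of approximation matters little.

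**The case against.** The strongest reply is that the opening condition of SAP 4.6.2 already refers to the protocol, and the protocol is arm-specific. Protocol 9.2 and 10.5 keep patients on the assigned strategy throughout. On that reading a PAV+ patient on PSV for a week has not stayed on protocol, and the list is shorthand for all the modes used in the trial. The remark that A/C is allowed in each arm fits this reading.

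Part of this stands. A reader might infer that crossovers are certain to remain in the per-protocol sample. The documents do not say so: the general condition permits exclusion by judgement, and a crossover patient may also leave through withdrawal or transfer. What does not stand is that the condition settles the matter, for the reason in step 3.

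Three further inferences are tempting but unsupported:

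- *That crossover goes uncounted in the deviation and DSMB reports.* SAP 4.5 carries no mode list. Its term can bear the ordinary meaning of a mode not allowed for that patient. Protocol 9.1 also collects use of A/C, PAV+ and PSV, and any deviations.
- *That agreement between the two analyses will be taken as proof that contamination was harmless.* Nothing gives the per-protocol set a decision role. SAP 4.6.1 says all analyses use the intention-to-treat sample, and SAP 6.1 to 6.6 assign no outcome to the per-protocol set.
- *That excluding crossovers would recover 1.30.* Crossovers may differ in how hard they are to wean, so removing them introduces post-randomization selection.

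**Conclusion.** The concern holds as a defect in the stated rule. The only operational mode criterion for the per-protocol sample ignores arm, conflicts with the protocol's arm-specific modes, and leaves crossover to an undefined condition. The per-protocol analysis may therefore keep crossovers and fail to address contamination.

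The reach is limited. The intention-to-treat analysis assigns patients to their randomized group "irrespective of compliance to their randomized group", so the primary result does not depend on this rule. The size of any dilution is unknown. The figure of about 1.27 at 10% crossover assumes a true hazard ratio of 1.30, crossover in the PAV+ arm only, full-time exposure to PSV, no residual PAV+ effect, and no exclusion of those patients by another route. Partial crossover would dilute less.

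**What to change.** In SAP 4.6.2, define non-protocolized mode by randomized arm, following the modes the protocol already sets:

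- PAV+ arm: any mode other than PAV+ or A/C.
- PSV arm: any mode other than PSV or A/C.
- Both arms: CPAP, T-piece and tracheostomy-mask time for the weaning tests is allowed.

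Keep the existing 48-hour limit and apply it to this definition. State in SAP 4.5 that the term has the same meaning there. In the adherence table and DSMB report, give the number of patients on the opposite arm's mode as a separate line, with hours where these can be derived.

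The change is mainly wording and alters no clinical rule. One point needs confirming. SAP 4.5 records duration only for non-protocolized modes, and Protocol 9.1 provides continuous ventilator data only at centres with the technical capability. The sponsor should therefore check that opposite-mode hours can be obtained from the recorded mode data. The per-protocol sample becomes slightly smaller and somewhat more selected after randomization, so it should remain supportive to intention-to-treat. SAP 2.6 holds analyses until the SAP is approved, so the definition should be settled before then.
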